### *Prestudy Data Collection and Training*

All anesthesiologists' level of expertise (post-graduate year or training) will be collected before starting the study as shown in Table 1. Patients' demographics will be collected and selected patient data will be recorded by the provider (see Table 2). This ensures that there are no

confounding factors in the difference in perceived ability to advance the epidural catheter among groups (i.e. morbid obesity or presence of known spinal deformities). This will be done in a coded manner, using a numerical code to be assigned to each individual study case. The master file will be kept in a locked filing cabinet in the principal investigator's office. All data will be analyzed in a coded fashion. Attention to strict confidentiality will be maintained; no attempts will be made to identify individual study subjects.

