### *Study Size*

In order to determine the study size, we looked at 114 consecutive epidural placements as part of our routine quality assurance with the Arrow® Epidural Catheterization Kit at Von Voigtlander. We found that in 11% (n=12) of epidurals placed, the epidural catheter did not thread on the first attempt. In a separate quality assurance check we retrospectively reviewed 100 epidural placements finding out that in 1% (n=1) of epidurals placed, the epidural catheter did not thread on the first attempt. A sample-size analysis for the primary outcome shows that 107 epidural placements per group would provide a power of 80% to detect a difference in proportion between the two techniques of 0.10 at the 0.05 level. Considering an attrition of 10-20% for follow-up and data missing, a total number of 240 epidural placements will be collected. Power calculations were computed using PASS 14.

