### *Statistical Analysis*

Statistical analysis will be performed using SAS 9.3 (SAS Institute, Cary, NC). The

primary outcome will be the success rate of epidural catheter threaded with each epidural kit, which will be compared by group using a chi-square test or Fisher's exact test, as appropriate. The secondary outcomes will be analyzed as follows: the difference in number of epidural attempts will be compared using the Mann-Whitney test; the difference in time to perform the epidural start to finish defined as the time the epidural needle is inserted through the patient's skin to the end of the catheter thread will be compared using the Student's t-test; the difference in the incidence of epidural needle manipulations once the epidural space has been established will be compared using the Chi-Square or Fisher's exact test, as appropriate; the difference in incidence of unintended dural puncture, paresthesia, and intravascular cannulations will be compared using the chi-square or Fisher's exact test, as appropriate. In addition, the difference in unsatisfactory labor analgesia with Arrow® and B.Braun® kits will be compared through the chi-square or Fisher's exact test, as appropriate, by looking at the difference in percentages of patients who have a verbal analogue pain score equal or less than 10 (scale 0 to 100) at 30 minutes following epidural medication administration. A p-value of 0.05 throughout will be considered statistically significant.

All statistical analyses will be performed using SAS 9.3 (SAS Institute, Cary, NC).

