## TABLES

**Table 1 Inability to advance epidural catheters according to physician level of training**

Physician level	Single-orifice Incidence	Multi-orifice Incidence	Statistics
First-year resident	x/X (x%)	x/X (x%)	p=
Second-year resident	x/X (x%)	x/X (x%)	p=
Third-year resident	x/X (x%)	x/X (x%)	p=
Fellow	x/X (x%)	x/X (x%)	p=
Attending	x/X (x%)	x/X (x%)	p=

Data are number (%).

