# SINGLE vs MULTI-ORIFICE CATHETER STUDY FORM

ANESTHESIOLOGIST CODE \_\_\_ Date \_\_\_ Time \_\_\_ room \_\_\_

Anesthesiologist : Attending Fellow CA-3 CA-2 CA-1

Patient Description Age: \_\_\_ Gest Age: \_\_\_ Ht/Wt: \_\_\_ G \_\_\_ P \_\_\_

Cervical dilation \_\_\_ cm Estimated Level of placement: L \_ - L \_

Relevant patient's comorbidities: \_\_\_\_\_

EPIDURAL KIT: ARROW BBRAUN

Time: loss of resistance to Epidural needle removed following successful placement \_\_\_ minutes : \_\_\_ seconds

Loss of Resistance Unable to get Loss Equivocal Loss Clear Loss

Dural Puncture epidural used ? YES NO

If Dural Puncture Epidural used, CSF in the spinal needle? YES NO

Dural Puncture Epidural used because of:  Equivocal loss  As part of technique

Because catheter wouldn't thread and wanted to make sure I was midline

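### Recording operator level and patient factors does not control confounding: every kit comparison is unadjusted, and a simple prespecified adjustment is available, chiefly useful for the time outcome

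*Combined protocol and SAP*

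**What the plan says.** Prestudy Data Collection and Training states that anesthesiologists' "level of expertise (post-graduate year or training) will be collected before starting the study as shown in Table 1", and that patient data will be recorded too. It then asserts "This ensures that there are no" "confounding factors in the difference in perceived ability to advance the epidural catheter among groups", giving morbid obesity and known spinal deformity as examples.

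Statistical Analysis contains no covariate, stratum or model. The primary outcome is the threading success rate, "which will be compared by group using a chi-square test" or Fisher's exact test. For the first secondary outcome, "the difference in number of epidural attempts will be compared using the Mann-Whitney test". Time is compared by Student's t-test, and the remaining outcomes by chi-square or Fisher.

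Operator level reappears only in Table 1, titled "Inability to advance epidural catheters according to physician level of training". It has five rows, each with its own p-value cell, and no pooled or stratified row. The study form records level for each placement ("Anesthesiologist : Attending Fellow CA-3 CA-2 CA-1"), together with height and weight.

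Under Randomization Procedure, one kit is assigned to each calendar week, with about 30 placements a week for about eight weeks. Placements are said to be shared fairly among residents, faculty and fellows. No balancing of operator level between kit weeks is described.

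**The concern.** The plan treats collecting possible confounders as if that dealt with them. Only the design or the analysis can do so, and here the analysis ignores them. Weekly randomisation protects on average, but about four weeks per kit leave room for chance differences in who is on service. If junior operators are slower or fail more often, a kit whose weeks had more of them would look worse with no true difference, and no planned analysis could separate the two.

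According to Objectives, the result is meant to guide which kit the hospital uses, and time to thread is the stated aim and hypothesis. An adjustment chosen after the data are seen would carry little weight. The five separate Table 1 tests do not help: each uses only a fraction of the data, and none gives an adjusted kit effect.

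**Working it through.** **The plan's own figure.** Study Size gives 107 per group for a difference in "proportion between the two techniques of 0.10 at the 0.05 level", with 80% power. The quality-assurance failure rates are 11% and 1%; the 11% is for Arrow, and the kit behind the 1% is not named. Two-sided, with pooled rate 6%:

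- n = [1.96·√(2·0.06·0.94) + 0.8416·√(0.11·0.89 + 0.01·0.99)]² / 0.10² = (0.658 + 0.276)² / 0.01 = 87.3.
- With continuity correction: (87.3/4)·[1 + √(1 + 4/(87.3·0.10))]² = 106.4, so 107. The figure reproduces.

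**Expected failures** at 120 per group: 120·0.11 + 120·0.01 = 13.2 + 1.2 = 14.4, or about 14.

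**Table 1 rows.** The plan gives no counts by level.

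- Equal fifths (assumption): 120/5 = 24 per kit, with 24·0.11 = 2.6 and 24·0.01 = 0.24 expected failures. Exact Fisher power for 11% vs 1% is 9%. It takes 5 vs 0 failures to reach significance (p = 0.0496); 4 vs 0 gives p = 0.109.
- A level with 40% of placements (assumption): 48 per kit, Fisher power 32%.

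**Time outcome, no kit effect.** All inputs except 120 per kit and eight weeks are assumptions: four weeks per kit, first-year share with mean m and weekly SD s, first-years slower by δ minutes, residual SD σ = 4 minutes.

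- Variance the t-test assumes: V₀ = [σ² + δ²·m(1−m)]·2/120.
- Actual variance: V₁ = [σ² + δ²·(m(1−m) − s²)]·2/120 + δ²s²·2/4.
- False-positive rate: 2·[1 − Φ(1.96·√(V₀/V₁))].

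| m | s | δ (min) | V₀ | V₁ | False positives |
|---|---|---|---|---|---|
| 0.40 | 0.20 | 3 | 0.303 | 0.477 | 12% |
| 0.40 | 0.10 | 2 | 0.283 | 0.302 | 6% |
| 0.40 | 0.30 | 4 | 0.331 | 1.027 | 27% |
| 0.20 | 0.05 | 3 | 0.291 | 0.302 | 5.4% |
| 0.20 | 0.10 | 3 | 0.291 | 0.334 | 6.8% |

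Simulation of the same set-up agrees: about 12% in the first row, and about 5.6% to 6.5% for the last two (repeat runs varied between roughly 5% and 7%). With operator level in a linear model the rate returns to about 5%, because level is the only source of week-to-week difference here.

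**Primary outcome, no kit effect.** Assume m = 0.40, s = 0.20, and failure 12% for first-years vs 2% for others, so 0.4·12 + 0.6·2 = 6% overall.

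- SD of the kit difference due to weekly mix: 0.10·0.20·√(2/4) = 1.4 percentage points.
- Ordinary sampling SD of the difference: √(0.06·0.94·2/120) = 3.1 points.
- By simulation, false positives are about 8% with uncorrected chi-square and about 4.5% with Fisher (another run gave 7.5% and 3.9%).

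**Cost of stratifying the primary test.** In simulation at 120 per group and 11% vs 1%, a Cochran-Mantel-Haenszel test over five levels has power 0.95, as does the crude chi-square. Its type I error is 0.048 to 0.052.

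**The case against.** The kit is randomised by week, so operator mix is balanced in expectation and an unadjusted primary test is a legitimate choice. That stands: the point is a false assurance and a missed improvement, not an invalid primary test.

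The inputs by level are not in the documents, and the plan describes placements as fairly shared. That also stands. Under a 20% first-year share with little weekly variation, the excess error for time is slight.

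Three stronger readings are tempting but not supported:

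- **That the primary comparison is seriously biased.** Mix imbalance adds an SD of 1.4 points to a sampling SD of 3.1, and Fisher's test stays below 5%. Crude chi-square error of up to 15% can be produced, but only by imposing a strong difference in level mix between the kits; weekly randomisation alone does not imply it.
- **That Table 1 carries a large multiplicity error.** Five tests at 0.05 have a nominal family-wise rate of 1 − 0.95⁵ = 22.6%, but Fisher's test at 24 vs 24 and a 6% failure rate has an actual error of only 0.6%. The weakness is lack of information, and Statistical Analysis rests no conclusion on those cells.
- **That everything needed for full adjustment is recorded.** The form has one operator level per placement and no field for who made the first attempt or for a handover. Spinal deformity could appear only in a free-text comorbidity line.

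Finally, excess error from week-to-week differences is partly a clustering problem. Adjusting for level removes only the part that runs through operator level.

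**Conclusion.** The point holds in a limited form. The assurance about confounding has no analysis behind it, and the five Table 1 tests do not supply one. The consequence is potentially material for time (about 6% to 27% false positives if first-years have a 40% share with weekly SD 10 to 30 points and are 2 to 4 minutes slower) and slight if operators are evenly spread. For threading success it is small. These sizes rest on assumed shares, weekly variation and differences by level, so they show what could happen and are not estimates for this service. The case for acting is that the adjustment uses data already collected, needs no extra placements, and is credible only if written down in advance.

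**What to change.** - Replace the sentence claiming that data collection rules out confounding with a prespecified adjustment rule.
- **Time:** use a linear model with kit, operator level as recorded on the form, and BMI computed from height and weight. Settle the time definition first: Statistical Analysis runs from skin insertion to end of threading, while the form runs from loss of resistance to needle removal.
- **Threading success:** report a Mantel-Haenszel risk difference stratified by the recorded operator level, collapsed to two or three groups (for example first-year resident, other residents, fellow or attending).
- **Table 1:** show counts by level, with the one stratified estimate in place of the five p-values.
- State that this is in addition to the handling of week clustering.

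The cost is a few sentences and minor programming. With about 14 expected failures, only one coarse factor is feasible for the primary outcome: a logistic model with kit and four level indicators would have fewer than three failures per parameter (14.4/5 = 2.9).

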### *Equipment, Technique and Study Data Collection*

There will be two epidural kits available for the study:

- 1) The FlexTip Plus® Epidural Catheterization Kit contains a 17 Gauge Tuohy needle, 8.9 cm long and a single open end hole FlexTip Plus® 19 Gauge flexible epidural catheter (Arrow International, Cleveland, OH).
- 2) The Perifix® FX Springwound Epidural Catheter Kit contains a 17 Gauge Espocan® Tuohy needle, 8.9 cm long and a closed tip multiport Perifix® FX Springwound 19 Gauge flexible epidural catheter (B.Braun Medical Inc., Bethlem, PA).

Both the Arrow® and B.Braun® epidural catheter kits are currently used at University of Michigan.

All patients will be in a sitting position. After standard sterile prep and drape, a wheal of local anesthetic will be applied to the interspace. An epidural Tuohy needle will be advanced through the *ligamentum flavum*. A syringe with saline will be attached to the epidural needle and

continuous or intermittent pressure will be applied to the syringe plunger until a drop in syringe pressure will be noticed (LOR).

Each time a skin wheal of local anesthetic is injected in patients' lumbar area, this will be counted as one epidural attempt. In addition, once loss of resistance has been established, if the epidural needle is withdrawn, redirected and re-advanced in order to get loss of resistance again because the clinician is not able to advance the epidural catheter, this will be considered as an additional epidural attempt.

Once, the epidural catheter has been threaded successfully, the clinician will apply negative pressure to the catheter through a syringe in order to rule out blood or cerebro-spinal fluid (CSF) aspiration. If aspiration of blood and CSF is negative, the patient will be given our standard medications consisting of 2 ml Lidocaine 1.5% with epinephrine 1:200,000 to rule out intrathecal catheter placement. Following 2 minutes, the patients will be given additional 3 ml from the lidocaine and epinephrine mixture in order to rule out intravascular cannulation. In addition, a standard loading bolus of bupivacaine 0.125% with fentanyl 3 mcg/ml will be administered in three fractionated doses of 5 ml each, through an epidural pump. All patients will be then connected to a programmed intermittent epidural bolus pump with the following settings: bupivacaine 0.125% with fentanyl 3 mcg/ml, programmed intermittent bolus 6 ml every 45 minutes. Patient's demand bolus 6 ml every 15 minutes, without baseline infusion.

If the epidural catheter cannot be sufficiently advanced into the epidural space, one or more of the following maneuvers will be adopted: additional saline will be administered through the Tuohy needle; alternatively, a new flexible epidural catheter can be inserted; if the catheter advances following one of these afore-mentioned maneuvers, the thread will be considered successful with minor adjustments. Conversely, if the needle is rotated, re-angled, redrawn and

re-advanced or advanced blindly, these will all be considered as major needle manipulations and recorded as failure of that attempt to advance the epidural catheter. Further attempts are made until proper epidural analgesia is established.

Establishment of successful labor analgesia will be defined at a verbal analogue score equal to or less than 10 on a 100-point scale within 30 min from the standard epidural medication administration. All data related to the technical aspects of the epidural placement will be collected in the form shown in the appendix. The goal of both study groups is the management of labor pain.

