## BACKGROUND

Identification of the epidural space involves recognition of a change in pressure from one tissue plane to another. This drop of pressure, called “loss of resistance” (LOR), across a band of connective tissue into the epidural space is detected using a needle-syringe apparatus. The operator applies pressure to the plunger of the syringe until the drop in pressure is identified when the plunger collapses. The epidural catheter, a small tube that is inserted into the epidural space to give the medication, is then advanced using the needle as a guide. Confidence in locating the epidural space is based on clarity of the loss of resistance and the ease of threading the epidural catheter.

When there is difficulty in advancing the epidural catheter after the epidural space has been identified, several maneuvers are performed in order to correct the problem. These include: injecting saline through the needle to “expand” the epidural space, advancing the needle tip 1-2 mm, inserting a new flexible epidural catheter, inserting a new non-flexible epidural catheter, rotating the needle bevel, changing a patient’s posture, pulling the needle back to re-engage the *ligamentum flavum* and then performing a second LOR technique, and removing the needle entirely and performing a new placement at the same or different interspace (1). Each time a new maneuver is performed, this is considered a new attempt at threading the epidural catheter into the epidural space. Not succeeding on threading the epidural catheter correctly into the epidural space on the very first try is considered a “failure to thread,” however these maneuvers are performed until adequate labor analgesia is established in all patients. Establishing labor analgesia on the first epidural catheter threading attempt reduces the amount of time between when the epidural is requested and when pain relief is administered. A “more successful”

epidural threading attempt is related to a decrease in the time required to thread the epidural and adequately relieve labor pain.

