## Ease of Threading the Epidural Catheter

- |   |                              |
|---|------------------------------|
|  Easy thread without further maneuvers  |                              |
|  hydrodissection, then catheter:  | Thread Did not thread |
|  new catheter from the same brand, then catheter:   | Thread Did not thread |
|  Rotated the needle, then catheter:   | Thread Did not thread |
|  Changed needle angle, then catheter:   | Thread Did not thread |
|  Withdrawal and re-advanced the needle with an additional LOR (this count as an additional attempt), then catheter: | Thread Did not thread |
|  Advanced the needle blindly, then catheter:  | Thread Did not thread |
|  Changed space  |                              |

Patient Comfort at 30 minutes (VAS  $\leq$  10/100) YES NO

Additional Number of attempts after loss of resistance 0 1 2 3 4 5

Complications (circle all that applies)

Wet tap Paresthesias Intravascular Other (please explain)

Epidural analgesia failed and then epidural Replaced? YES NO

Delivery date \_\_\_ and Time \_\_\_\_\_

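### The number of attempts has no single usable definition: Background and Methods count differently, and the study form cannot supply the Methods count

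*Combined protocol and SAP*

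**What the plan says.** Three places say how attempts are counted.

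- **Background.** After listing the corrective manoeuvres (saline, advancing the needle, a new catheter, rotating the bevel, changing posture, repeating loss of resistance, a new placement), it says: "Each time a new maneuver is performed, this is considered a new attempt at threading the epidural catheter into the epidural space".
- **Methods, Equipment, Technique and Study Data Collection.** "Each time a skin wheal of local anesthetic is injected in patients' lumbar area, this will be counted as one epidural attempt". One more is added "if the epidural needle is withdrawn, redirected and re-advanced in order to get loss of resistance again" because the catheter will not advance.
- **Study form, Ease of Threading the Epidural Catheter.** Of all the manoeuvres with a tick box, only one is labelled as adding to the count: "Withdrawal and re-advanced the needle with an additional LOR (this count as an additional attempt". A separate line asks for the additional attempts after loss of resistance, from 0 to 5, with no counting rule beside it. No field records the number of skin wheals.

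Two further places say what the count is for. The Objectives name the number of *threading* attempts as the primary outcome. Statistical Analysis makes the success rate primary and adds, as a secondary outcome, that "the difference in number of epidural attempts will be compared using the Mann-Whitney test". Table 2 also uses the term *epidural* attempts. No sentence says whether threading attempts and epidural attempts are one variable or two.

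**The concern.** The study asks which kit's catheter threads more easily. The Methods rule counts a second skin wheal made before the epidural space is found, when no catheter has yet been tried. It adds nothing for threading trouble that is resolved by saline, a new catheter or a rotation. The Background rule does the reverse on both points.

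Two clinicians with identical placements could therefore circle different numbers on the form, and an analyst could not tell which rule each had used. If the rule is settled only after the data are seen, the choice could steer the result.

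**Working it through.** **Step 1. Apply the rules to the same placements.** These are constructed examples. The last column takes the form's line as its own annotation suggests.

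| Placement | Background | Methods | Form: additional attempts |
|---|---|---|---|
| A. One wheal; saline, then rotation, then threads | 3 | 1 | 0 |
| B. Second wheal before any loss of resistance; then threads at once | 1 | 2 | 0 |
| C. One wheal; one repeated loss of resistance, then threads | 2 | 2 | 1 |

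One plus the form's number is 1, 1 and 2. That matches the Methods in A and the Background in B, so the form follows neither rule throughout. The Background count can be partly rebuilt from the ticked manoeuvres, but repeats of a manoeuvre and posture changes have no field. The Methods count cannot be rebuilt. The box for a changed space shows that another space was used, but it gives no number of wheals and sits among the threading items.

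**Step 2. The plan's own figure.** Study Size gives 107 per group for 11% v 1%, 80% power and a 0.05 level. A two-sided calculation without correction needs [1.96√(2×0.06×0.94) + 0.8416√(0.11×0.89 + 0.01×0.99)]² / 0.10² = 87.35 per group. With the continuity correction this becomes (87.35/4)[1 + √(1 + 4/(87.35×0.10))]² = 106.4, rounded up to 107. The figure reproduces, so the sample size is not in question here.

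**Step 3. How far the rule can move the result.** Inputs from the plan: 120 per kit (Randomization Procedure); 11% and 1% not threading on the first attempt (Study Size). These give 0.11×120 ≈ 13 and 0.01×120 ≈ 1 difficult placements.

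Assumptions:
- The 1% belongs to B.Braun. Study Size does not name the kit in that review.
- The planning rates follow the Background rule. Study Size does not define first attempt.
- Of the 13, 8 took two attempts and 5 took three.
- The number needing a repeated loss of resistance is unknown, so a range is shown.
- Placements are independent, as the planned test treats them.

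The tie-corrected Mann-Whitney test, without continuity correction, uses z = (U − 7200)/SD. Here 7200 = 120×120/2 and SD² = (120×120/12)[241 − Σ(t³ − t)/(240×239)], where t are the tie sizes.

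- *Every manoeuvre counts* (8 with two and 5 with three, v 1 with two). U = 8×119 + 5×120 + ½(107×119 + 8×1) = 7922.5. Ties are 226, 9 and 5; SD = 218.4; z = 722.5/218.4 = 3.31; **p = 0.0009**. Scoring all 13 as two attempts gives p = 0.001, so the 8/5 split hardly matters.
- *Only repeated loss of resistance counts* (k v 0). U − 7200 = 60k.

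| k v 0 | U − 7200 | SD | z | p |
|---|---|---|---|---|
| 6 v 0 | 360 | 145.4 | 2.48 | **0.013** |
| 4 v 0 | 240 | 119.2 | 2.01 | **0.044** |
| 3 v 0 | 180 | 103.5 | 1.74 | **0.082** |

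If the single B.Braun case also counts, 10 v 1 gives p = 0.006 and 6 v 1 gives p = 0.056. The same difficult placements can thus fall on either side of 0.05, depending on the rule and on a share that the documents do not give.

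**The case against.** The best defence is that the Background is narrative and the Methods govern. On this reading *threading attempt* and *epidural attempt* are different things. Statistical Analysis and Table 2 use the Methods' term, and the form's one annotation agrees with the Methods on repeated loss of resistance. Most of the operational text does then point to the Methods rule. Two gaps remain: the wheal half of that rule cannot be obtained from the form, and the threading-attempts count named in the Objectives has no analysis as a count.

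It is also fair to say that threading trouble is not lost to the trial. The success rate, the needle manipulations, Table 3, the recorded time from loss of resistance and the tick boxes all capture it. The harm is confined to one outcome.

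A reader might infer three stronger things that the documents do not support:

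- *That wheals swamp the count, so that it mostly measures difficulty in finding the space.* Assuming 18 of 120 second wheals in each arm would raise the 4 v 0 case to p = 0.49. But the documents give no wheal rate, and the form's count starts after loss of resistance, so wheals before that point would not enter it.
- *That the Methods contain a third counting rule.* The same section says that, after saline or a new catheter, "if the catheter advances following one of these afore-mentioned maneuvers, the thread will be considered successful with minor adjustments", while rotation, re-angling or blind advance is "recorded as failure of that attempt to advance the epidural catheter". This sorts manoeuvres into minor and major for the success and manipulation outcomes. The remark that further attempts follow describes care and assigns no number.
- *That the sample size or the success-rate comparison fails for this reason.* The 107 reproduces. How success is scored, and which outcome is primary, are separate questions.

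**Conclusion.** The inconsistency is real and should be corrected before data collection. The plan has two stated rules for counting attempts, a form that follows neither in full, and two names for the outcome with nothing to separate them. Followed as written, the Methods rule gives a count that cannot be collected and that does not match the threading attempts named in the Objectives.

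The size is an illustration, not an estimate. It rests on the assumptions listed with the calculation, above all the unknown share of difficult placements that need a repeated loss of resistance. At 4 v 0 or 6 v 0 the difference stays below 0.05 under the narrower rule; at 3 v 0 or 6 v 1 it does not. That the Methods rule counts *only* wheals and repeated loss of resistance is an inference, since the text does not say so, but the form's single annotation supports it. The effect falls on the attempts count, which Statistical Analysis lists as secondary.

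**What to change.** Adopt one definition and use it in the Background, Objectives, Equipment section, Statistical Analysis, Table 2 and form:

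*Number of threading attempts = tries at advancing the catheter after the first loss of resistance; each manoeuvre followed by a new try adds one.*

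- Print this beside the form's existing line for additional attempts after loss of resistance, and score the outcome as 1 plus that number.
- Take skin wheals out of this outcome.
- Keep the minor/major split for the success and manipulation outcomes.
- Report repeated loss of resistance separately from its existing tick box, so that the distinction between it and a simple adjustment is kept.

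The cost is wording and re-briefing the clinicians who complete the form. There are real drawbacks. The count weights a saline flush the same as a repeated loss of resistance, the form's line stops at 5, and a new field is needed if wheals are to be reported. The change concerns recording and analysis only and does not touch how placements are managed.
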